2. STUDY OBJECTIVES AND ENDPOINTS

2.1. Objectives

Primary Objective

- To estimate the Maximum Tolerated Dose (MTD) and select the Recommended Phase 2 Dose (RP2D) for the combination of PF-05082566 with MK-3475 in patients with advanced solid cancer.

Secondary Objectives

- To evaluate the overall safety profile;
- To characterize the single dose and multiple dose pharmacokinetics of PF-05082566 and MK-3475 given in combination following IV administration;
- To evaluate the immunogenicity of PF-05082566 and MK-3475 when given in combination;
- To assess the anti-tumor effect of PF-05082466 in combination with MK-3475 (by RECIST criteria);
- **Expansion Cohorts Only:** To characterize the mechanism of sensitivity and/or resistance to PF-05082566 in combination with MK-3475 in tumor tissue.

CCI

- CCI

- CCI

2.2. Endpoints

Primary Endpoint

- First 2 cycles Dose-Limiting Toxicity (DLT) of PF-05082566 in combination with MK-3475.

Secondary Endpoints

- Adverse events as characterized by type, frequency, severity (as graded by NCI CTCAE v.4.03), timing, seriousness and relationship to study therapy PF-05082566 in combination with MK-3475;

- Laboratory abnormalities as characterized by type, frequency, severity (as graded by NCI CTCAE v.4.03);
- Vital signs, weight, ECOG Performance Status;
- PK parameters of PF-05082566 and MK-3475, including but not limited to C_{max} , C_{trough} , T_{max} , AUC_{0-last} , $AUC_{0-\infty}$, CL and Vd (as data permits);
- Anti-Drug Antibody levels for PF-05082566 and MK-3475;
- Objective tumor response by Response Evaluation Criteria in Solid Tumors (RECIST) v1.1;
- Time-to-response (expansion cohorts only);
- Duration of response (expansion cohorts only);
- Progression-free survival (expansion cohorts only);
- **Expansion Cohorts Only:** Paired de novo tumor biopsy collection at sequential time points for analysis of exploratory mechanistic biomarkers such as IHC assessment of tumor-infiltrating lymphocytes, quantitation of T cell receptor sequences, and gene expression.

CCI

- CCI

- CCI

3. STUDY DESIGN

3.1. Study Overview

This is a Phase 1b, open-label, multi-center, multiple-dose, safety, pharmacokinetic CCI study designed to estimate the maximum tolerated dose (MTD), and determine the Recommended Phase 2 Dose (RP2D) of PF-05082566 in combination with MK-3475 in patients with advanced solid tumors.

PF-05082566 will be administered as a 1-hour intravenous infusion q3wks. On Day 1 of each dosing cycle, in which the drugs are co-administered, the MK-3475 infusion will start 30 minutes after completion of PF-05082566 infusion and after the post- PF-05082566 and pre-MK-3475 PK blood samples are drawn.

A maximum of 45 patients will be treated during the dose escalation phase of this study.

Treatment with study drugs will continue until completion of 32 cycles (approximately 24 months) of treatment, confirmed objective disease progression, patient refusal, patient lost to follow up, unacceptable toxicity occurs, or the study is terminated by the Sponsor, whichever occurs first.

Safety will be monitored at regular intervals throughout the study by means of laboratory tests and clinical visits.

Antitumor activity will be assessed by radiological tumor assessments conducted at baseline, at 9 weeks, and every 6 weeks thereafter, whenever disease progression is suspected (eg, symptomatic deterioration), at the time of End of Treatment (if not done in the previous 6 weeks), and during follow-up visits, using RECIST version 1.1.

Discontinuation from treatment may be considered at the investigator's discretion for patients who have attained a confirmed complete response (CR), that have been treated for at least 24 weeks on study, and have at least two treatments with MK-3475 and PF-05082566 beyond the date the initial CR was declared. Patients who then experience radiologic disease progression will be eligible for treatment with both study drugs at the discretion of the investigator and by the approval of the Sponsor, if no cancer treatment was administered since the last dose of study drugs, the patient meets the safety parameters listed in the Inclusion/Exclusion criteria, and the trial is open. Patients will resume therapy at the same dose and schedule at the time of initial discontinuation. Patients who complete a maximum number of 32 cycles (approximately 24 months) on study treatment and demonstrate clinical benefit with manageable toxicity and are willing to continue receiving the study treatment will be given the opportunity to continue treatment upon agreement between investigator and sponsor.

CCI

In addition, patients with RECIST defined disease progression who are continuing to derive clinical benefit from the study treatment will be eligible to continue treatment with PF-05082566 plus MK-3475 provided that the treating physician has determined that the benefit/risk for doing so is favorable. (Refer to [Section 5.3.4](#) and [Section 7.4.1](#) for details). Also in this case, the maximum period on-treatment will be 32 cycles (approximately 24 months).

[figure not shown]
After estimation of the MTD for the combination on the q3wk schedule, PF-05082566 may be co-administered along with MK-3475 to study safety and tolerability on an alternative dosing schedule for both drugs. Other study drug doses may also be tested based on emerging safety and tolerability data. The initiation of additional patient cohorts to explore

additional dosing schedules or study drug doses will be done at the discretion of the Sponsor, and can occur in parallel with enrollment of patients in expansion cohorts on the q3wk dosing schedule.

In addition, once the MTD of PF-05082566 administered in combination with MK-3475 has been estimated with confidence, one or more expansion cohorts of patients with selected advanced solid tumors will be enrolled to further study the safety, tolerability, PK **CCI** and preliminary anti-tumor activity for PF-05082566 in combination with MK-3475 to support RP2D selection, as well as to study tumor-associated biomarkers. The tumor types for further study could include NSCLC and potentially other tumor types based on emerging data from the dose escalation phase of this study.

PK/Anti-Drug Antibody (ADA) sampling will be required for all patients (See [Table 3](#) and [Section 7.2](#) for details). No drug interaction is anticipated between PF-05082566 and MK-3475. Since PF-05082566 and MK-3475 are eliminated via a non-specific catabolic degradation process, it is unlikely that concomitant medication can alter its clearance even if target expression is affected. To assess any potential interactions, steady state pharmacokinetics and the formation of anti-drug antibodies will be monitored for both the agents and compared with historical data.

For all patients in dose-expansion cohorts, a de-novo biopsy will be required at study entry followed by a second biopsy at the time of first follow up scans at 9 weeks (after 3 cycles of treatment). Optional de novo biopsies may be collected for patients in dose-escalation cohorts to support the assessment of disease progression. **CCI**

3.1.1. Starting Dose

The PF-05082566 starting dose is 0.45 mg/kg (see [Section 1.3](#)). The starting dose of MK-3475 will be 2 mg/kg (see [Section 1.3](#)). Both study drugs will be administered on a q3wk schedule. See [Section 1.3](#) for more details.

3.2. Criteria for Dose Escalation

No dose escalation of MK-3475 is foreseen for the estimation of the combination MTD. Dose escalation and de-escalation of PF-05082566 will follow the Time-to-Event Continual Reassessment Method (TITE-CRM) (Cheung and Chappell, 2000)³ up to 5.0 mg/kg. The first three patients (first cohort) will be treated at the starting dose. For each subsequent patient, the probability of DLT is estimated for each level based on all the collected data from all treated patients up to that time and the prior expectations of toxicity, and the patient is assigned to the currently estimated target level (with escalation restrictions as indicated

below), defined as the dose having an estimated probability of DLT closest to but not greater than the target rate (25%). The probabilities of toxicity are estimated based on a Bayesian statistical model to learn about the overall dose-toxicity relationship. Patients' DLT data will be reported to the study statistician who will update the dose-toxicity model before the next enrolled patient is treated.

The MTD is defined as the highest combination dose with a DLT rate <25% from the model estimate (explained in [Section 9.2](#)).

Dose escalation stops if:

- Maximum sample size (n=45, see [Section 9.3](#)) is reached; or
- 9 evaluable patients have been treated at the estimated MTD; or
- All doses appear to be overly toxic and the MTD cannot be determined in the current trial.

In the TITE-CRM paradigm, patients who have enrolled in the trial, but have not experienced DLT, will be included in the probability calculation with an initial weight equal to the proportion of the 6-week (2 cycles of PF-05082566 and MK-3475) DLT observation period that the patients have completed (however, the weight function may be modified if accumulating safety data in suggest a different pattern). Patients who experience DLT or complete the observation period without DLT will be assigned full weight (=1). Details on the TITE-CRM method are provided in [Section 9.2](#) and the Statistical Analysis Plan.

To avoid overly rapid escalation and to retain the efficiency of dose administration when enrollment is fast, the following restrictions and practical considerations will be followed.

- Dose skipping in escalation to untested doses is not allowed ($k \rightarrow k+1$). In particular, at least three patients should have been treated at dose level k before escalation to dose level $k+1$;
- At least three patients should have been on treatment (for a minimum of 3 weeks or 1 cycle) and observed DLT rate <33% at dose level k before a patient is assigned to dose level $k+1$ (*Note that the waiting window depends on our knowledge in the time-to-event pattern of toxicity and accumulating safety data, and thereby the confidence in the associated weights. However, intentional delay in enrollment in the absence of DLT or serious AEs should be minimized and discouraged*);
- Dose escalation recommendation by the TITE-CRM algorithm may be overruled by the sponsor if the nature of the existing data causes safety concern.

Dose escalation and de-escalation will be carried out according to [Table 1](#). Intra-patient dose escalation will not be permitted.

Cumulative safety data will continue to be evaluated at the estimated MTD using the Bayesian statistical model. Should emerging data in the expansion cohort indicate the selected dose is more toxic than previously estimated (>25%), or in the case of an exposure plateau or biomarker saturation (eg, sCD137) the next lower dose or an intermediate dose level will be explored, and may be declared as the RP2D.

For the first cohort there will be a minimum 7-day window between the first dose of a patient and the first dose of the next patient. For the first 3 patients enrolled in additional dose escalation cohorts, a minimum 24-hour time window will apply between their first doses. There will be no required time window between first doses for patients enrolled in dose cohorts with at least 3 previously treated patients.

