Antitumor activity will be assessed by radiological tumor assessments conducted at baseline, at 9 weeks after the first dose of study drug, and every 6 weeks thereafter, whenever disease progression is suspected (eg, symptomatic deterioration), and at the time of End of Treatment/Withdrawal (if not done in the previous 6 weeks), using RECIST version 1.1. Safety will be monitored at regular intervals throughout the study by means of laboratory tests and clinical visits. Pharmacokinetic CCI blood endpoints will also be monitored in all patients.

For all patients in dose-expansion cohorts, a de novo biopsy will be required at study entry followed by a second biopsy at the time of the week 9 scans (after 3 cycles of treatment). Optional de novo biopsies may be collected from patients in dose-escalation cohorts to support the assessment of disease progression. CCI

Study Treatments:

PF-05082566 will be administered as a 1 hour intravenous infusion q3wks in escalating doses and may include the following planned doses: 0.20 mg/kg, 0.45 mg/kg, 0.9 mg/kg, 1.8 mg/kg, 3.6 mg/kg, and 5 mg/kg. The starting dose of PF-05082566 will be set at 0.45 mg/kg.

MK-3475 will be administered as a 30 minutes IV infusion at a dose of 2 mg/kg q3wks. This MK-3475 dose was chosen based on PK, safety, and efficacy considerations (see [Section 1.3](#) for more details).

After estimation of the MTD for the combination on the q3wk schedule, PF-05082566 may be co-administered along with MK-3475 to study safety and tolerability on an alternative

dosing schedule for both drugs. Other study drugs doses may also be tested based on emerging safety and tolerability data. The initiation of additional patient cohorts to explore additional dosing schedules or study drugs doses will be at the discretion of the Sponsor.

CCI

Therefore, patients with RECIST defined disease progression who are continuing to derive clinical benefit from the study treatment will be eligible to continue treatment with PF-05082566 plus MK-3475 provided that the treating physician has determined that the benefit/risk for doing so is favorable. The duration of treatment will be up to 32 cycles (approximately 24 months) in all patients.

Dose escalation and MTD estimation for the PF-05082566 plus MK-3475 combination will be conducted according to the following algorithm:

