- a. Dose escalation and de-escalation of PF-05082566 follows the Time-to-Event Continual Reassessment Method (TITE-CRM) up to a maximum dose of 5.0 mg/kg q3wk.
- b. The MTD is defined as the highest combination dose with a DLT rate <25% from the model estimate.
- c. Dose escalation stops if:
 - Maximum study sample size is reached; or
 - 9 evaluable patients have been treated at the estimated MTD; or
 - All doses appear to be overly toxic and the MTD cannot be determined in the current trial.

Treatment with study drugs will continue until completion of 32 cycles (approximately 24 months) of treatment, disease progression (RECIST v. 1.1), patient refusal, unacceptable toxicity occurs, or the study is prematurely terminated by the Sponsor; whichever comes first. Discontinuation from treatment may be considered at the investigator's discretion for patients who have attained a confirmed CR, have been treated for at least 24 weeks on study, and have at least two treatments with MK-3475 and PF-05082566 beyond the date the initial CR was declared. Patients who then experience radiologic disease progression will be eligible for re-treatment with both study drugs at the discretion of the investigator and by the approval of the Sponsor, if no cancer treatment was administered since the last dose of study

drugs, the patient meets the safety parameters listed in the Inclusion/Exclusion criteria, and the trial is still open. Patients will resume therapy at the same dose and schedule at the time of initial discontinuation. Patients who complete a maximum number of 32 cycles (approximately 24 months) on study treatment and demonstrate clinical benefit with manageable toxicity and are willing to continue receiving the study treatment will be given the opportunity to continue treatment upon agreement between investigator and sponsor.

Dose Escalation Criteria:

Based on the starting dose example above, dose escalation and de-escalation will be carried out according to Table 1.

Table 1. Dose Escalation Cohorts

Dose Escalation Cohort	PF-05082566	MK-3475
-1	0.20 mg/kg q3wks	2 mg/kg q3wks
1 (Starting Dose Level)	0.45 mg/kg q3wks	2 mg/kg q3wks
2	0.9 mg/kg q3wks	2 mg/kg q3wks
3	1.8 mg/kg q3wks	2 mg/kg q3wks
4	3.6 mg/kg q3wks	2 mg/kg q3wks
5	5 mg/kg q3wks	2 mg/kg q3wks

* q3wks: every 3 weeks

SCHEDULE OF ACTIVITIES:

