5.3. Administration

A cycle is defined as the time from Day 1 dose to the next Day 1 dose of PF-05082566. If there are no treatment delays, a cycle will be 3 weeks in duration.

All trial treatments will be administered on an outpatient basis. After Cycle 1, study drugs may be administered up to 2 days before or after the scheduled treatment day of each cycle

for administrative reasons. Patients will be observed in the clinic for at least 2 hours after each infusion of study drug.

All patients should be weighed within 72 hours prior to dosing for every cycle to ensure they did not experience either a weight loss or gain >10% from the prior weight used to calculate the amount of study drug required for dose preparation. Decision to recalculate the study drug dose based on the weight obtained at each cycle can be in accordance with institutional practice, however if the patient experienced either a weight loss or gain >10% compared to the weight used to calculate the initial dose, the amount of study drug required for preparation and administration for the current cycle must be recalculated using this most recent weight obtained.

The study drug dose escalation levels are shown in [Table 1](#). In addition, doses of PF-05082566 and MK-3475 available for dose modification according to guidelines in [Section 5.3.7](#), are shown below in [Table 7](#).

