5.3.7. Dose Reductions

After the first two cycles (the DLT evaluation period), dose reductions in PF-05082566 and/or MK-3475 may be required based on the worst toxicity experienced in the previous cycle (see [Table 8](#)).

No specific dose adjustments are recommended for Grade 1/2 treatment-related toxicity. However, investigators should always manage their patients according to their medical judgment based on the particular clinical circumstances.

Patients experiencing recurrent and intolerable Grade 2 non-hematologic toxicity may resume dosing, with specific dose modifications detailed in [Section 5.3.7.1](#), once recovery to \leq Grade 1 or baseline is achieved. For guidance on dosing following immune related toxicities, see [Section 5.3.7.2](#).

Patients requiring dose reductions in PF-05082566 may be decreased one dose level (see [Table 7](#)). Patients treated at 2 mg/kg MK-3475 may be dose reduced to 1mg/kg due to AEs possibly attributed to MK-3475 alone. Once a patient has a dose reduction in PF-05082566 or MK-3475 for a drug-related toxicity, the dose will not be re-escalated. Patients requiring more than one dose reduction will be withdrawn from treatment unless otherwise agreed between the investigator and the Sponsor.

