5.3.7.1. Study Drug Dose Modification Guidelines

[Table 7](#) below shows the PF-05082566 and MK-3475 doses available for this study. Suggested dose modification guidelines are presented in [Table 8](#) below. Both study drugs should be held for the listed toxicities with dose modifications as suggested. For information

on the management of immune-related adverse events (see [Section 5.3.7.2](#) below). Patients requiring dose reductions in PF-05082566 due to dose-limiting toxicities may have study drug doses decreased one dose level (see Table 7). MK-3475 may be dose-reduced to 1 mg/kg due to AEs which may be recurrent or intolerable (beyond the DLT evaluation period) and possibly related to MK-3475, rather than PF-05082566, based on emerging safety and tolerability data.

Table 7. Available Dose Levels

PF-05082566*	MK-3475
50 mg/kg	2 mg/kg
3.6 mg/kg	1 mg/kg
1.8 mg/kg	
0.9 mg/kg	
0.45 mg/kg	
0.20 mg/kg	

Table 8. Dose Modification Guidelines for Treatment Related Adverse Events

Toxicity	Grade	Hold Treatment (Both Drugs)	Criteria for Treatment Restart (Both Drugs)	Dose Modification (Both Drugs*)	Discontinue Patient (after consultation with Sponsor) (Both Drugs)
Hematologic Toxicity meeting any of the DLT criteria in Section 3.3	3	Yes	Resolved to Grade 1 or better	Decrease dose by one dose level (based on Table 1).	If toxicity does not resolve within 9 weeks of last infusion, consider permanent discontinuation after consultation with the sponsor.
	4	Yes	Resolved to Grade 1 or better	Decrease dose by one dose level (based on Table 1).	If toxicity does not resolve within 9 weeks of last infusion, consider permanent discontinuation after consultation with the sponsor.
Non-Hematologic toxicity (other than immune-related toxicities described in Section 5.3.7.2 , 5.3.7.3 , 5.3.7.4)	1 and 2 (if not recurrent/intolerable)	No	N/A	Continue at same dose level.	N/A
	2 (recurrent/intolerable)	Consider withholding	Resolved to Grade 1 or better	Continue at same dose level. (reference Section 5.3.7.3 for recommendations regarding pneumonitis and Section 5.3.7.1 for guidance on reduction of the MK-3475 dose.	If toxicity does not resolve to Grade 1 or better within 9 weeks of last infusion, consider permanent discontinuation after consultation with the sponsor.

Toxicity	Grade	Hold Treatment (Both Drugs)	Criteria for Treatment Restart (Both Drugs)	Dose Modification (Both Drugs*)	Discontinue Patient (after consultation with Sponsor) (Both Drugs)

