9.2. Statistical Methods for Dose Allocation: TITE-CRM

A number of alternative designs have been proposed to the standard 3+3 design for Phase I dose escalation trials that improve its accuracy, efficiency and statistical validity, including the continual reassessment method (CRM),¹⁷ and its variants.

Delayed-onset toxicities are a particular challenge for phase I trials of combination therapies.¹⁴ Most of the available dose-escalation designs, including the 3+3 design, the up-and-down designs and the CRM design, require all patients to have completed a fixed

observation period for toxicity (eg, 1-2 cycles of the experiment regimen, or 6-8 weeks after start of treatment) before additional cohorts of patients can be enrolled. Thus, trial accrual is patient to opening and closing which may pose logistical risk on the success and completion of the study. In addition, patients who are either lost to follow-up or die of events unrelated to treatment are usually required to be replaced. Due to these reasons, the trial duration could be unacceptably long in case of prolonged observation window and unexpected high rate of patient drop-out.

The time-to-event continual reassessment method (TITE-CRM), a variant of the original CRM method, is open to accrual continually, and maintains other advantages of the CRM relative to the 3+3 design. Like CRM, TITE-CRM seeks to determine the target MTD dose, defined as the dose most closely identified with the target rate, which is the largest acceptable DLT rate determined by the investigators based on the relative costs and benefits of the treatment.

TITE-CRM is to be implemented as described by Cheung et al.³ and Normolle et al.¹⁵ for the dose-escalation of PF-05082566. PF-05082566 may be administered intravenously at the following available dose levels of 0.20, 0.45, 0.9, 1.8, 3.6, and 5 mg/kg on an every 3 week schedule (q3wk). PF-05082566 will be co-administered with MK-3475 on Day 1 of each treatment Cycle. MK-3475 will be administered at 2 mg/kg, MK-3475 will be administered q3wk. Higher dose levels may be available based on the emerging safety data from single agent PF-05082566 dosed at 5 mg/kg in the Phase 1 first-in-human study. The MTD is defined as highest dose that is associated with a DLT rate $\leq 25\%$. A power function modeling DLT rate at each dose d_i ($i=1, \dots, 6$) expressed as $\Pr(\text{DLT} \mid d_i) = F_i(\beta)$ will be used:

[figure not shown]
$$F_i(\beta) = p_i^{\exp(\beta)}$$

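### Table 7 of the protocol lists 50 mg/kg as the top PF-05082566 level, while every other dose list stops at 5 mg/kg: a tenfold discrepancy in one cell of the dose-modification table

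*Protocol*

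**What the plan says.** **Where the top level is 5 mg/kg.** Section 3.2 of the protocol sets the escalation range "up to 5.0 mg/kg. The first three patients (first cohort) will be treated at the starting dose". The algorithm in the Protocol Summary words the limit as "up to a maximum dose of 5.0 mg/kg q3wk", and the summary's treatment paragraph lists the planned doses as "0.20 mg/kg, 0.45 mg/kg, 0.9 mg/kg, 1.8 mg/kg, 3.6 mg/kg, and 5 mg/kg". Table 1 has 5 mg/kg as cohort 5. Section 9.2 gives the same six levels for the TITE-CRM model and adds that higher levels might become available, depending on single-agent data at 5 mg/kg; it names none. In the SAP, the cohort lists in Sections 3.4.1 and 5.2, the model description in 5.1.2 and the exposure derivations in 6.5.3 and 6.5.3.1 all end at 5 mg/kg.

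**Where it is 50 mg/kg.** Section 5.3.7.1 says that Table 7 "below shows the PF-05082566 and MK-3475 doses available for this study". Its PF-05082566 column reads 50, 3.6, 1.8, 0.9, 0.45 and 0.20 mg/kg.

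**How the tables are used.** Section 5.3 states "The study drug dose escalation levels are shown in" Table 1, and then names Table 7 for dose modification. Section 5.3.7 states "Patients requiring dose reductions in PF-05082566 may be decreased one dose level" and refers to Table 7. Sections 5.3.7.1 and 5.3.7.2 refer to Table 7 for the same step. Table 8 and its footnote key that reduction to Table 1.

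**The concern.** Table 7 is a working table that sites are told to consult when they change a dose, and its introduction presents it as the study's list of doses. As printed, its top row is ten times the highest level found anywhere else, and a patient treated in cohort 5 cannot be located in it. The one-level reduction is governed by two tables that disagree on what the top level is. At stake is a dosing or transcription error if someone takes the top row of Table 7 at face value, in a dose-finding study of a combination.

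**Working it through.** No sample-size or power calculation bears on this. The check compares the dose lists and then follows each written rule that uses them.

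**1. The lists side by side (mg/kg).**

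| Level | Table 1, Protocol Summary, Section 9.2, SAP | Table 7 | Match |
|---|---|---|---|
| -1 | 0.20 | 0.20 | yes |
| 1 | 0.45 | 0.45 | yes |
| 2 | 0.9 | 0.9 | yes |
| 3 | 1.8 | 1.8 | yes |
| 4 | 3.6 | 3.6 | yes |
| 5 | 5 | 50 | no |

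Both lists have six entries, and the model in Section 9.2 indexes six doses. The 50 therefore stands in the place of the 5; it is not a seventh level. It cannot be obtained from any other dose list in either document.

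**2. Size of the discrepancy.** 50 / 5 = 10.

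Per infusion, at an assumed body weight of 70 kg: 50 × 70 = 3,500 mg against 5 × 70 = 350 mg. The documents give no weight. Over 50 to 100 kg the figures run from 2,500 mg against 250 mg to 5,000 mg against 500 mg.

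Against the protocol's own overdose definition (Section 8.4, more than 20% above the prescribed dose), the threshold for a 5 mg/kg prescription is 5 × 1.2 = 6 mg/kg. A dose of 50 mg/kg would exceed that prescription by (50 − 5) / 5 = 900%.

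**3. Spacing of the levels.** Ratio of each level to the one below:

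- Table 1: 0.45/0.20 = 2.25; 0.9/0.45 = 2.0; 1.8/0.9 = 2.0; 3.6/1.8 = 2.0; 5/3.6 = 1.39.
- Table 7: 2.25; 2.0; 2.0; 2.0; 50/3.6 = 13.89.

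Only the last ratio differs.

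**4. Can any written rule lead to 50 mg/kg?**

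- Escalation between cohorts follows Table 1, and untested levels may not be skipped (Section 3.2).
- A patient's own dose may not be escalated (Section 3.2).
- The sponsor gives the site each patient's dose level in writing before dosing (Section 5.1).
- Table 7 is cited for modification, reductions go one level down, and a reduced dose is not raised again (Section 5.3.7).
- One level below the top row is 3.6 mg/kg in Table 7 and also in Table 1.

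None does.

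**5. Does any planned analysis read Table 7?**

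- Exposure uses the administered dose divided by weight, from the dosing eCRF pages (SAP 6.5.3 and 6.5.3.1).
- Relative dose intensity divides by an intended dose taken from a fixed list that ends at 5 mg/kg (SAP 6.5.3.1).
- Treatment groups are the six cohorts of SAP 3.4.1.
- DLTs are defined in SAP 3.1 and summarized by those groups (SAP 6.1.1.1).

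None does.

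**The case against.** The strongest reply is that 50 may be 5.0 with its decimal point lost. The text was read from PDF by a program, and the protocol writes this dose as 5.0 mg/kg in Section 3.2 and in the Protocol Summary. This cannot be excluded, and the source must be looked at before anything else. It does not dispose of the point: the other five rows of the same column kept their decimals, and 5.0 was read correctly in those two places. If the source reads 5.0, the contradiction disappears and only the split citation between Tables 1 and 7 remains.

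The second reply is that other controls contain the error. This largely stands. A reader might infer that a patient following the protocol could be given 50 mg/kg, or that a cohort 5 patient could not be stepped down. The documents do not support either. Cohort doses come from Table 1 and the sponsor's written assignment, Table 8 already points to Table 1, and the step from the top is the same in both tables. These controls lower the chance of harm but do not remove the conflicting figure.

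The third reply is that 5 mg/kg is not an absolute ceiling, since Section 9.2 leaves room for higher levels and other passages allow further doses to be tested. That is correct, and 5 mg/kg is best described as the highest planned level. But no passage names 50 mg/kg, and Table 7 presents it as already available.

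**Conclusion.** The contradiction holds on the text as supplied. One cell of Table 7 differs tenfold from every other statement of the top PF-05082566 level, and the 5 mg/kg level is absent from that table. It needs correction because of where it stands, in a table that sites are told to use when modifying doses. The risk is residual: it depends on someone acting on the printed top row despite the written assignment and Table 1.

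A reader might also infer damage to exposure summaries, relative dose intensity or the attribution of DLTs at the top level. The documents do not support this, because none of those derivations uses Table 7.

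The conclusion assumes that the source PDF prints 50. The milligram figures also rest on assumed body weights; the tenfold ratio does not. Which entry is right is for the sponsor to settle. The finding is only that the passages disagree and must be reconciled.

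**What to change.** 1. Check the top row of Table 7 in the source PDF for a lost decimal point.
2. If 50 is confirmed, reconcile that row with Table 1, Sections 3.2 and 9.2 and the SAP cohort list, so that all dose lists carry the same levels.
3. Have the dose-reduction text in Sections 5.3, 5.3.7, 5.3.7.1 and 5.3.7.2 and Table 8 cite the same table for a one-level reduction.
4. Notify sites of the correction.

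The cost is one table cell, a few cross-references and an administrative letter or an entry in the next amendment. The design, the sample size and the analyses do not change.
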